5.6 CRITERIA FOR WITHDRAWAL OF PATIENTS AND PROCEDURES TO FOLLOW

Patients can leave the study at any time, without having to give no explanation. Additionally, patients may be withdrawn from the study for the following reasons:

1. They have adverse events that affect participation in the study

2. They do not wish to continue (withdrawal of consent) for any reason.

3. Violation of protocol or significant deviation from specific procedures

of the study

4. Loss of follow-up

5. Appearance of a clinically significant intercurrent disease that affects the participation in the study.

6. The investigator considers that it is beneficial for the patient to withdraw from the study. The withdrawal of the patient from the study will not represent for him any type of damage in the control of their disease, in subsequent treatments or in the treatment to be received by the doctor. If a patient is withdrawn from the study at any time the reason must be recorded in the corresponding sheet of the data collection notebook (CRD). Patients who are withdrawn from the study due to an adverse event or abnormal results of laboratory values should be followed up to total trial resolution or for a period of time considered clinically reasonable by the researcher.

Patients withdrawn from the trial due to an adverse event will be included in security analysis. Patients who have undergone surgically intervened for graft insertion. If a patient is lost, an attempt should be made to contact him. The investigator it should reflect the loss of follow-up in the medical history.

The aim of the study is to obtain 12 evaluable patients in each trial arm (24 in total). A patient will be considered evaluable as long as it has been infiltrated into the space intervertebral a dose of MSV or belongs to the control group. In the event that for some cause the application cannot be made to an included patient, another must be included patient in the same group until reaching the 12 patients treated in each arm of the clinical trial. The study exit and the causes of the study exit of the initial patient and no further follow-up will be necessary since they will not have received the Trial treatment.

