Antibiotic prophylaxis will be performed with 2 g of IV cefazolin or 1 g of IV vancomycin in case allergy. The implantation of the cells is carried out under light sedation and radiological control. The cells are injected by puncture of the disc avoiding the neurovascular elements (Konings & Veldhuizen, 1988). After double brushing the region with a aqueous solution of povidone jodine (or chlorhexidine in patients allergic to iodine), The field is delimited with sterile sheets and local anesthesia (Scandicain 1%) is applied to the skin, subcutaneous tissue and muscle near the puncture. With fluoroscopy in position anteroposterior, a vertical line is marked on the skin corresponding to the projection of the spinous process with a sterile dermographic pencil. Then a line is drawn perpendicular corresponding to the projected image of an aligned Kirschner wire with the intervertebral space to be treated and a 20G spinal needle is inserted with an inclination 25 to 35 degrees toward the midline at a point 8 to 9 cm (depending on the patient morphotype) from the midline. At this time, fluoroscopy is switched to lateral position to ensure needle penetration follows the correct direction until the nucleus pulposus is reached. After verifying the correct position of the needle in the nucleus pulposus both in the anteroposterior fluoroscopic view and in the side, the cell suspension is slowly injected. Using this procedure, do not we had incidents in none of the 10 patients in our previous study (Orozco et al., 2011).

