8.4 Serious Adverse Event (AAG)

8.1.4.1 Definition

A Serious Adverse Event is any unfavorable medical event that any dosage of the product or due to specific study procedures:

□ Produces the death of the patient,

□ Threatens life,

□ Produces permanent or significant disability,

□ It gives rise to hospitalization or prolongation of it, (hospitalizations scheduled prior to patient selection or study procedures, will not be considered AAG).

□ Congenital anomalies and malignant processes.

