11.3.1 Evaluable patients

A patient will be considered evaluable provided that he has undergone the specified interventions (Control or allogeneic MSV).

11.3.2 Efficacy population (Per protocol (PP) population):

Secondary efficacy endpoint analysis will be based on all patients who do not have incurred in major protocol violations, and have at least one rating final efficacy of the graft.

11.3.3 Safety population:

It is the population that includes all evaluable patients who have undergone one of the three study treatments. The security population will be the population of analysis of the safety variables of the treatment.

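### The safety population can leave out patients whose treatment procedure was started but not completed, and the plan's rules for including and following them disagree

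*Combined protocol and SAP*

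**What the plan says.** Section 11.3.3 defines the safety set: "It is the population that includes all evaluable patients who have undergone one of the three study treatments". It then fixes its use: "The security population will be the population of analysis of the safety variables of the treatment". The trial has two arms, so three treatments is a slip.

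Evaluable is defined twice. Section 11.3.1 requires that the patient has had the control or the MSV intervention. Section 5.6 (in the closing part, which the table of contents appears to list as 5.7) counts a patient "as long as it has been infiltrated into the space intervertebral a dose of MSV or belongs to the control group". Under that wording an MSV patient qualifies by receiving the dose, and a control patient by group membership.

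The same part of 5.6 replaces, within the same group, any included patient in whom the application cannot be made, until 12 per arm are treated. Of the patient replaced it says "no further follow-up will be necessary since they will not have received the Trial treatment".

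Other text points the other way:
- Section 5.6, on withdrawal: "Patients withdrawn from the trial due to an adverse event will be included in security analysis".
- Section 5.8: patients with adverse events are followed until resolution or stability, even after leaving the study.
- Section 8.3: all adverse events are logged from consent, whatever their cause.

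**The concern.** The main objective (3.1) is the viability and safety of percutaneous injection into the disc. A procedure that is begun and abandoned is direct evidence on both. If such patients are left out of the safety set and replaced, the headline safety result describes only procedures that succeeded.

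The exposures that come before the injection are not trivial by the protocol's own account. Sections 2.6.3 and 6.1.5 describe the expected complications as those of discography, with discitis the most serious. Section 8.2 lists sedation risk, infection, bruising and death among the risks of the treatment procedure. The reason given for dropping follow-up, that no trial treatment was received, takes no account of these exposures.

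With 12 patients per arm, one omitted patient can separate a report of no serious events from a report of one.

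**Working it through.** **Plan figure.** There is no derived figure to reproduce. Sections 5.4 and 11.1 fix 12 + 12 = 24 without a power calculation, event rate or rate of stopped procedures. The check is therefore a comparison of rules, followed by an illustration.

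**Order of exposure (6.1.3).** Antibiotic prophylaxis is given, and "The implantation of the cells is carried out under light sedation and radiological control". Local anaesthesia, needle insertion and fluoroscopic confirmation that the needle is in the nucleus follow. The cells are injected last. A patient can therefore be sedated and punctured without being treated.

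**The rules applied to four cases.**
1. *Never taken to the procedure* (for example, no usable cell batch). Outside the safety set, replaced, not followed. There was no procedural exposure, so the rule is reasonable.
2. *Started, stopped because of an adverse event.* Outside the set under 11.3.1 and 11.3.3. Inside the safety analysis under the withdrawal rule in 5.6, and followed under 5.8. Nothing says which rule prevails.
3. *Started, stopped for another reason, no event that day.* Outside the set, with no further follow-up needed. The safeguards in 5.6 and 5.8 are not triggered, because there is no event yet. The yearly checks in 5.8 are for those who received cell therapy, and the card in 5.9 is for those who received study medication. No planned contact remains.
4. *Completed.* Inside the set.

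Case 2 is a contradiction. Case 3 is a gap.

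**Size, as an illustration.** Suppose 12 MSV patients are treated with no serious adverse event (SAE), and one further procedure was started and stopped with an SAE. Exact (Clopper-Pearson) 95% intervals:
- Treated set: 0/12 = 0%. Upper limit 1 − 0.025^(1/12) = 26.5%.
- Started set: 1/13 = 7.7%. Lower limit 1 − 0.975^(1/13) = 0.2%. Upper limit, the 97.5% point of Beta(2, 12), = 36.0%.
- With two such patients: 2/14 = 14.3% (1.8% to 42.8%).

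**A condition on that illustration.** The main safety variables in 11.2.1 are the number of SAEs related to study medication and the percentage of patients with a related SAE. A patient who received no study injection may have an SAE that is not counted as related. Changing the population alone could then give 0/13.

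**How often a stop might occur.** With an assumed stop rate f, the chance of at least one stop in 12 attempts is 1 − (1 − f)^12:

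| Assumed f | Chance of at least one stop |
|---|---|
| 1% | 11% |
| 2% | 22% |
| 5% | 46% |
| 10% | 72% |

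These rates are assumptions. The documents give only that the earlier study had no incidents in 10 patients.

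**Scale of case 3 for discitis alone.** The protocol puts discitis below 0.1%. Even at f = 10%, 12 attempts give 12 × 0.10 = 1.2 stopped procedures and fewer than 1.2 × 0.001 = 0.0012 expected cases.

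**The case against.** The strongest reply is that the worrying case is already covered. A procedure stopped by a serious complication is naturally a withdrawal for an adverse event. Section 5.6 then puts the patient in the safety analysis, 5.8 requires follow-up, 8.3 requires logging, 8.1.4.2 requires notification within one working day, and 11.3.6 lists all events. Sedation and antibiotic reactions mostly show at once, so these rules would catch them. What remains is a late complication after a stop for some other reason, and for discitis the expected number is very small. The replacement clause can also be read as meant for patients who never reach the procedure. A fragment directly after the inclusion rule in 5.6, about patients who had the implantation, is incomplete and may have widened that rule.

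Much of this stands. A reader might infer that harms in stopped procedures go unrecorded; sections 5.8 and 8.3 say otherwise. A reader might also see a conflict with the SAE definition, which covers events from "any dosage of the product or due to specific study procedures". There is none: that text says which events are serious, not who is analysed.

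The reply does not remove the inconsistency. Section 11.3.3 is the rule that sets the denominator, and it contains no exception for patients withdrawn before the injection. The replacement clause applies to any cause and does not separate patients never started from those started and stopped. Logging an event does not place the patient in the analysed set.

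**Conclusion.** The point holds as a contradiction between rules plus a narrow follow-up gap. Followed as written, 11.3.3 makes the main safety and feasibility result conditional on the procedure having been completed. The loss is mainly from the analysed result rather than from the record.

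Its likelihood cannot be stated, because no stop rate is given. The change from 0/12 to 1/13 shows what one omitted patient would do. It is not an expected effect, and it also requires that procedure-related SAEs count in the numerator.

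A reader might infer that the loss falls only on the MSV arm, because only that needle must reach the disc. The documents do not settle this. The summary, 4.2 and 6.1 place the control injection in paravertebral muscle, but 4.1 says that in both cases the product goes to the nucleus pulposus area. Controls are to undergo the same manoeuvres, and 11.3.3 requires treatment in both arms. What the text does show is an unequal definition in 5.6: infiltration for MSV, membership for control.

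**What to change.** 1. In 11.3.3, define the safety population as all randomised patients in whom any V1 study procedure (prophylaxis, sedation or needle) was started, analysed by arm, whether or not the injection was completed. Use one definition of evaluable in 5.6 and 11.3.1.
2. Report the numbers of started and completed procedures in each arm as denominators. This also serves the feasibility objective.
3. In 11.2.1, extend the main safety variables to SAEs related to study medication or to study procedures. Without this, the first change may not alter the result.
4. Reconcile the no-follow-up sentence in 5.6 with 5.8 for procedures started and then stopped. The follow-up schedule itself is for the sponsor to decide.
5. Correct three study treatments to two.

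The cost is protocol and analysis-plan wording, plus whatever follow-up the sponsor sets for these patients. The downside is small: the reported event rate may be slightly less favourable. The change should be made in advance, because follow-up that was not collected cannot be recovered and a denominator chosen after the events are known would carry little weight.

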11.3.4 Analysis methods

Descriptive statistics will be made including summary statistics and lists. For the comparisons of means at 0, 6 and 12 months a comparison of means using the t-test or Wilcoxon test as appropriate (see 11.2).

11.3.5 Background and demographic characteristics

Lists by patient of all demographic measures and baseline data will be presented, tabulating the following numerical variables: number of valid cases, number of values not available, mean, standard deviation, 95% confidence interval of the mean, median, minimum and maximum. For the discrete and categorical variables, will present the frequency and percentage of each value.

11.3.6 Security

□ AA and AAG lists will be made showing relationship, causality and severity.

□ Frequency and percentage of AAG

□ Frequency and percentage of AA

□ Laboratory parameters including hematology and biochemistry: leukocytes, absolute neutrophil count, platelet count, creatinine, AST (SGOT) / ALT (SGTP), etc. Laboratory parameters will be listed by patient and visit and include the reference range values. These parameters are will be summarized by baseline and post-baseline visit analysis. The analysis will include "n" valid, mean, standard deviation, median, minimum and maximum. In addition, the change from baseline will be evaluated as described in 11.2. All the Statistical analyzes will be performed with a bilateral significance level of 0.05.

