7.2 TEST SCHEDULE

VER TABLA EN LA PAGINA SIGUIENTE

CRONOGRAMA	Preinclusión	Inclusión	Tratamiento	Seguimiento (m=meses)			
PROGRAMA DE VISITAS:		V0	Día 1 V1	Día 8 V2	3 m V3	6 m V4	12 m V5
Historia Clínica y Exploración Física	x	x		x	х	x	x
Entrega de la Hoja de Información	x						
RX Columna Lumbar Simple y dinámica	x					x	x
Firma del Consentimiento Informado		x					
Serologías víricas preceptivas		X					
Comprobación de criterios de Inclusión y Exclusión		x					
RM lateral, T2, cuantitativa		x				x	x
EVA, Oswestry, SF-12		X			х	x	x
Tratamiento control o con MSV alogénicas*			**X				
Analítica Control		x		x		x	x
VISITA:		0	V1	V2	V3	V4 M	V5 12 M

* Las MSV deben haberse obtenido del donante y expandido en la ventana temporal adecuada. **RX en quirófano para guiar y seguir aplicación. La RM de Vo se usará también

para valorar la integridad del anillo fibroso externo.

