11.2 STATISTICAL METHOD USED

In all descriptive analyzes, categorical variables will be summarized using frequencies and category percentages. For the distributions of continuous variables, will present the mean and its Standard Deviation, the median and the 25th and 75th percentiles of the distribution, the number of cases, minimum and maximum value.

All hypothesis tests will be two-tailed, with a significance level of 5%. The The result of a hypothesis test will comprise the 95% Confidence Interval of the variable (s) analyzed. To calculate the statistical significance of the differences between the two groups, a normality analysis of the distribution will be carried out and compare the means using the double-tailed t-test or the Wilcoxon, depending on whether the population is Gaussian or not.

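### Laboratory changes are tested at an unadjusted 0.05 over an unstated number of tests, and no by-arm summary of out-of-range values is planned

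*Combined protocol and SAP*

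**What the plan says.** Section 11.3.6 covers hematology and biochemistry. It names "leukocytes, absolute neutrophil count, platelet count, creatinine, AST (SGOT) / ALT (SGTP), etc", which is six parameters and an open end. Three outputs are planned:

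- listings by patient and visit, with reference ranges;
- parameters "summarized by baseline and post-baseline visit analysis", with valid n, mean, standard deviation, median, minimum and maximum;
- in addition, "the change from baseline will be evaluated as described in 11.2".

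The section closes: "All the Statistical analyzes will be performed with a bilateral significance level of 0.05". Section 11.2, to which it refers, would "compare the means using the double-tailed t-test or the Wilcoxon, depending on whether the population is Gaussian or not". That sentence is written for differences between the two groups. Neither section mentions multiplicity, an exploratory status, or a rule for reading the p-values.

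The documents do not agree on timing. The row "Analítica Control" in the section 7.2 schedule is marked at V0, V2 (day 8), V4 (6 months) and V5 (12 months). The visit text in 7.2.1 names a post-treatment laboratory control only at Visit 2. Section 11.3.4 describes comparisons of means at 0, 6 and 12 months.

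**The concern.** Safety is part of the main objective, and the trial has 12 patients per arm. Testing many laboratory changes at 5% each, with no adjustment, can produce significant results when nothing has changed. A reader of the report could not tell these from real effects, because the plan does not fix how many tests were to be done.

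A test of means or ranks is also a poor instrument for laboratory toxicity, which usually appears as a large change in one or two patients and not as a shift of the whole group. The reference ranges are collected for the listings but are not used in any summary by arm. The only formal comparison of the arms on laboratory data is therefore the one least suited to the question.

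**Working it through.** **The plan's own figure.** The only error rate stated is 0.05 two-sided per test (11.2 and 11.3.6, which agree). No overall rate is given. The 12 per arm in 11.1 was fixed without a calculation, so there is nothing further to reproduce.

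**Inputs.** Six named parameters (11.3.6). One post-baseline laboratory visit (7.2.1), two time points (11.3.4) or three visits (7.2). One family of tests (between arms), or two (within each arm).

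**Formulas.** With m tests and no true change, the expected number of false positives is 0.05 × m, whatever the correlation. The chance of at least one is 1 − 0.95^m if the tests are independent. Correlation lowers that chance. It was simulated for the three-visit readings with 4,000 runs, 12 per arm and t-tests. Assumed correlations were 0 to 0.5 between parameters and 0.5 to 0.8 between visits.

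| Reading, six parameters | m | Expected false positives | At least one, independent | At least one, correlated |
|---|---|---|---|---|
| One visit, one family | 6 × 1 = 6 | 0.3 | 1 − 0.95^6 = 26.5% | not simulated |
| Two time points, one family | 6 × 2 = 12 | 0.6 | 1 − 0.95^12 = 46.0% | not simulated |
| Three visits, one family | 6 × 3 = 18 | 0.9 | 1 − 0.95^18 = 60.3% | 38% to 56% |
| Three visits, within each arm | 18 × 2 = 36 | 1.8 | 1 − 0.95^36 = 84.2% | 62% to 82% |

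The open-ended list pushes these figures up. If 10 or 15 parameters are assumed at three visits in one family (30 or 45 tests), the chance is 79% or 90% under independence. Across the two counts it is 50% to 87% under the same correlations.

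**Sensitivity to one abnormal patient.** Suppose one of 12 patients changes by x, large against the noise, and the others do not change.

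- Within the arm, the mean is x/12. The sum of squares is x² − x²/12 = 11x²/12, so the variance is x²/12 and the standard error is x/12. Hence t = 1 however large x is, against a critical value of about 2.2 on 11 degrees of freedom.
- Between arms, the pooled variance is (11x²/12)/22 = x²/24. The standard error is √(x²/24 × 2/12) = x/12, and again t = 1.
- A Wilcoxon test only gives that patient the highest rank.

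A simulation agrees. It used assumed ALT values: baseline 25, upper limit of normal 40, SD of change 8. With one patient at 3, 5 or 10 times the upper limit, the t-tests rejected in under 0.2% of runs and the Wilcoxon tests in about 3% to 5%, no more than chance.

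**The case against.** The strongest reply is that the tests are an addition to a plan that already looks at individuals. Section 11.3.6 lists every value by patient and visit with its reference range and reports the minimum and maximum. Section 8.1 counts an altered laboratory parameter as a possible adverse event, section 8.2 says events may be detected in laboratory tests, and adverse events are listed and tabulated. A reader might infer that a marked abnormality could go unnoticed behind a non-significant mean. The documents do not support that: with 12 per arm it would be visible in these outputs. What remains is that no table counts such patients by arm.

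A reader might also infer that every parameter is tested at every visit, or in each arm. That is a reasonable reading of a by-visit analysis, but it is not stated. Section 11.2 describes a between-group test, so the 36-test figures rest on a within-arm reading that 11.3.6 leaves open. Independence is also unlikely: AST and ALT, or leukocytes and neutrophils, tend to move together, and all changes share one baseline. It is therefore not established that a false signal is more likely than not on the between-arm reading with six parameters.

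The laboratory p-values are, moreover, supportive. Section 11.2.1 names related serious adverse events as the safety variables, and no stated decision depends on a laboratory test. In a small early trial, unadjusted testing at least errs towards flagging. These points limit the importance of the finding, but they do not supply the missing label, the number of tests or the by-arm summary.

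**Conclusion.** The point holds as a modest improvement to safety reporting and does not threaten the trial's validity. Section 11.3.6 plans laboratory tests at 0.05 with no adjustment, over a set of parameters, visits and comparisons that the documents leave open. With the six named parameters, the chance of at least one false signal runs from 26.5% (one visit, one family, independent tests) to 84% (three visits, both arms, independent tests). The three-visit single family lies between, at 38% to 60%. These figures assume no true change, tests that hold their nominal level, and the correlations stated above; a longer parameter list raises them.

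The tests are also insensitive to one marked abnormality. The listings, extremes and adverse event route cover that at patient level, so the gap is one of summary and comparison and not of detection.

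**What to change.** In 11.3.6, replace the laboratory significance tests with tables by arm. These would be shifts from baseline against the reference range, or counts of patients who move outside it at any post-baseline visit, placed next to the planned listings. Present mean changes descriptively. Label any confidence interval or p-value that is kept as exploratory and unadjusted. Exchanging p-values for unadjusted 95% intervals would not be enough by itself, because an interval that excludes zero is the same signal as p below 0.05.

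Close the parameter list, and state which visits and which comparisons (within arm, between arms) apply. Sections 7.2, 7.2.1 and 11.3.4 must be reconciled on laboratory timing for this purpose.

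The cost is a change of wording and different tables from data already planned. The downside is that no formal laboratory p-values would be available.
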